10.1.3.2 Time at risk (days)

Definitions for time at risk (days) are provided as follows:

- For participants who complete the Maintenance Treatment Period as planned and continue into an extension study (and, therefore, do not have the SFU visit in the feeder study):
 - Final visit date – Date of first dose + 1.
- For participants who die prior to the final visit:
 - Date of death – Date of first dose in the + 1.
- For all other participants, use the minimum of the following:
 - Date of last dose – Date of first dose + 141 days.
 - Date of last clinical contact – Date of first dose + 1.

Note: This group could include participants who discontinue early, participants who complete the Maintenance Treatment Period as scheduled but choose not to continue into an extension study, or participants who are ongoing in the SFU period at the time of the data snapshot (in the case of the interim analysis).

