10.2.1 Data considerations

Treatment-emergent AEs are defined as those AEs that have a start date on or following the first dose of study treatment through the final dose of study treatment + 140 days (covering the 20-week SFU period). If it is not possible (due to partial dates) to determine whether or not an AE is treatment-emergent then it will be assumed to be a TEAE.

An AE will be assigned to the Initial Treatment Period if it started between the first administration of IMP on Day 1 up to Week 16. An AE will be assigned to the Maintenance Treatment Period if it started between the Week 16 study drug administration and Week 48.

If an AE occurs on the date of a treatment switch, the event is attributed to the original treatment. The only exception to this is if the AE fulfills any of the criteria specified below:

- Events that fulfill the anaphylaxis criteria for acute events (refer to Appendix A in Section 12.1)
- Hypersensitivity events identified by the SMQ “Hypersensitivity (SMQ)” (see Section 12.1 Appendix A)
- Events with an high level term (HLT) of “Administration site reactions NEC”
- Events with an HLT of “Injection site reactions”

The rules for imputing partial start or stop dates are outlined in Section 4.2.4.

Any TEAEs that occur during the SFU Period will be attributed to the period in which the participant was before initiating the SFU Period.

Duration of AEs will not be calculated if there is missing stop date information.

If the intensity of an AE is unknown, it is considered as severe. If the relationship to study drug is missing, it is considered as related. Note that if the seriousness of an adverse event is unknown, every attempt should be made to resolve this prior to a snapshot for an interim analysis or database lock; in the exceptional case that the seriousness of an adverse event is still missing then no imputation should be applied for this characteristic.

Adverse events will be presented as “number of participants (percentage of participants) [number of events]”. In this style of output, “[number of events]” will include all cases of an AE including repeat occurrences in individual participants, while “number of participants” will count each participant only once.

Subject time at risk represents the time a participant is at risk for having an AE. The definitions for subject time at risk (in days) are outlined in Section 10.1. These definitions will be used for exposure-adjusted AE summaries.

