Selected AE summaries will include the exposure-adjusted incident rate (EAIR) with associated 95% CI and the exposure adjusted event rate (EAER).

The EAIR is defined as the number of participants (n) with a specific AE adjusted for the exposure and will be scaled to 100 subject-years:

$$EAIR = 100 \times n / \sum_{i=1}^N (T_{Exp(i)})$$

Where $T_{Exp(i)}$ is the exposure time and N is the number of participants at risk.

If a participant has multiple events, the time of exposure is calculated to the first occurrence of the AE being considered. If a participant has no events, the total time at risk is used.

Exact Poisson 95% confidence intervals for incidence rates are calculated using the relationship between the Poisson and the Chi-square distribution (Ulm, 1990; Fay and Feuer, 1997):

$$LCL = \chi^2_{2n, \alpha/2} / 2$$

$$UCL = \chi^2_{2(n+1), 1-\alpha/2} / 2$$

where n is the number of participants with a specific AE for the incidence rate of interest and is the basis for the number of the degrees of freedom for the chi-square quantile for the upper tail probability χ^2 .

The EAER will be the number of AEs including repeat occurrences in individual participants divided by the total time at risk scaled to 100 patient-years and calculated using:

$$EAER = 100 \times N_{AE} / \sum_{i=1}^N (T_{Risk(i)})$$

where N_{AE} is the total number of AEs, T_{Risk} is the time at risk for each participant, and N is the total number of participants at risk.

No confidence interval will be computed for EAER.

Selected summaries, as specified in Section 10.2.2, will include the risk difference between bimekizumab and placebo. The risk difference is calculated as:

$$RD = IP_{BKZ} - IP_{PBO}$$

where IP_{BKZ} is the incidence proportion for the bimekizumab-treated group and IP_{PBO} is the incidence proportion for the placebo group. Note that incidence proportion simply refers to the percentage of participants within the specified treatment group that experienced a given adverse event.

The standard error for the risk difference is calculated as follows:

$$SE_{RD} = \sqrt{\left(IP_{BKZ} \times \left(\frac{1 - IP_{BKZ}}{n_{BKZ}} \right) \right) + \left(IP_{PBO} \times \left(\frac{1 - IP_{PBO}}{n_{PBO}} \right) \right)}$$

where n_{BKZ} is the number of participants in the bimekizumab-treated group and n_{PBO} is the number of participants in the placebo group.

The corresponding confidence interval for the risk difference is as follows:

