10.2.2 AE summaries

The following summaries will be provided by treatment group for the Initial Treatment Period, and the Initial and Maintenance Treatment Period combined based on the SS, and AMS respectively. In addition, all summaries of TEAEs based on “100 subject years” will include EAIR (with 95% confidence interval) and EAER. For AEs that emerged after 112 days but still within the 140 days window, those AEs would be classified as TEAE. These AEs will be excluded from the outputs based on the Initial Period but included in the AE summaries for Initial and Maintenance Treatment Period.

- Incidence of TEAEs – Overview
- Incidence of TEAEs per 100 subject years by SOC, HLT, and PT
- Incidence of Serious TEAEs per 100 subject years by SOC, HLT, and PT
- Incidence of TEAEs Leading to Study Participant Discontinuation per 100 subject years by SOC, HLT, and PT
- Incidence of TEAEs Leading to Death by SOC, HLT, and PT
- Incidence of TEAEs by Maximum Relationship by SOC, HLT, and PT
- Incidence of Serious TEAEs by Relationship SOC, HLT, and PT – Note: For EudraCT reporting purposes
- Incidence of Related Serious TEAE by SOC, HLT, and PT
- Incidence of Severe TEAE per 100 subject years by SOC, HLT, and PT

- Incidence of TEAEs Leading to Death by Relationship by SOC, HLT, and PT – Note: For EudraCT reporting purposes
- Incidence of TEAEs by Maximum Severity, SOC, HLT, and PT
- Incidence of TEAEs by decreasing frequency of PT
- Incidence of TEAEs Above Reporting Threshold of 5% by SOC and PT
- Incidence of Non-Serious TEAEs by SOC, HLT, and PT
- Incidence of Non-Serious TEAEs by Maximum Relationship SOC, HLT, and PT
- Incidence of Non-Serious TEAEs Above Reporting Threshold of 5% by SOC and PT
- Incidence of Non-Serious TEAEs Above Reporting Threshold of 5% by Relationship SOC and PT
- Incidence of Related TEAEs per 100 subject years by SOC, HLT, and PT
- Incidence of Related TEAEs Above Reporting Threshold of 5% by SOC and PT
- Incidence of TEAEs – Suspected and Confirmed COVID-19 cases by SOC, HLT and PT
- Incidence of TEAEs Excluding TEAEs Exclusively Related to COVID-19 Vaccine by SOC, HLT, and PT
- Incidence of TEAEs Exclusively Related to COVID-19 Vaccine by SOC, HLT, and PT
- Incidence of COVID-19 Vaccine Interval Censored TEAEs by SOC, HLT, and PT
- Incidence of COVID-19 Vaccine Interval TEAEs by SOC, HLT, and PT

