Suspected and confirmed COVID-19 cases will be identified with the preferred terms “Corona virus infection” or “Corona virus test positive”.

The following subset of tables will also be presented for the Maintenance Treatment Period using the MS:

- Incidence of TEAEs – Overview
- Incidence of TEAEs per 100 subject years by SOC, HLT, and PT
- Incidence of Serious TEAEs per 100 subject years by SOC, HLT, and PT
- Incidence of TEAEs Leading to Discontinuation per 100 subject years by SOC, HLT, and PT
- Incidence of TEAEs Leading to Death by SOC, HLT, and PT

The following tables will be presented for the Initial Treatment Period:

- Incidence of TEAEs Above Reporting Threshold of 5% with Risk Differences by SOC and PT
- Incidence of Serious TEAEs and Risk Differences by SOC and PT

The following table will be presented for the combined Initial and Maintenance Treatment Period. This summary will include only AEs that occur while a participant is on bimekizumab.

Any AEs in the Initial Treatment Period that begin while a participant is on placebo will be excluded.

- Incidence of TEAEs per 100 subject years by SOC, HLT, and PT and by Time of Onset Relative to Anti-bimekizumab Antibody Status. This will include columns for the following:
 - TEAEs starting before the first ADAb positive result (includes ADAb categories 2 and 5) where TEAEs have occurred before the following events: a) the first positive ADAb result for subjects in category 2 and b) the first post-Baseline boosted ADAb titer result for subjects with titer results and the first post-Baseline positive ADAb result for subjects with positive ADAb at Baseline with no other samples with titer available for subjects in category 5
 - TEAEs starting on the same date or after the first ADAb positive result (includes ADAb Categories 2, 3, 4, 5 and 6) where TEAEs have occurred on or after the following events: a) the first positive ADAb results for subjects in categories 2, 3, 4 and 6, and b) the first post-Baseline boosted ADAb titer result for subjects with titer results and the first post-Baseline positive ADAb result for subjects with positive ADAb at Baseline with no other samples with titer available for subjects in category 5
 - TEAEs for subjects who are ADAb negative at all timepoints (includes ADAb Category 1)

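### The adverse-event table by onset relative to antibody status splits events at the first positive result but not time at risk, so the 'before' and 'on or after' rates are understated; retained placebo time also lowers every column in the placebo-switch arm

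*SAP*

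**What the plan says.** Section 10.2.2 of the SAP lists one table for the combined Initial and Maintenance Treatment Period: "Incidence of TEAEs per 100 subject years by SOC, HLT, and PT and by Time of Onset Relative to Anti-bimekizumab Antibody Status". It has three columns.

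- Events before the first positive result. This column holds Categories 2 and 5, cut at the first positive result (Category 2) or the first boosted titer (Category 5).
- Events on or after that date. This column holds Categories 2, 3, 4, 5 and 6.
- Events in participants who are negative throughout (Category 1).

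Events that begin while a participant is on placebo are left out of this table.

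The same section says that "all summaries of TEAEs based on “100 subject years” will include EAIR (with 95% confidence interval) and EAER". Section 10.2.1 sets the denominator: "The definitions for subject time at risk (in days) are outlined in Section 10.1. These definitions will be used for exposure-adjusted AE summaries". It divides the EAER by total time at risk. For the EAIR it stops exposure at the first occurrence in participants with the event, and otherwise "If a participant has no events, the total time at risk is used".

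For the combined period, Section 10.1.3.2 gives "Final visit date – Date of first dose + 1" for participants who enter the extension study. For most others it gives the smaller of last dose minus first dose plus 141 days and the span to last clinical contact. Neither it nor Sections 9.3.2, 10.2.1 or 10.2.2 cuts time at an antibody result or starts it at the first bimekizumab dose.

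**The concern.** The numerator is divided carefully, down to which titer counts as boosted, while the denominator stays whole. A Category 2 or 5 participant contributes the same full time at risk to both the 'before' and the 'on or after' column. That includes time in which no event could have entered the column.

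This is the plan's table for judging whether adverse events become more frequent once antibodies appear. If the 'on or after' rate is deflated, a real increase can be reduced or hidden, which is the unsafe direction for a safety display.

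A second mismatch works the same way. On-placebo events are removed, but the time at risk of participants who switch from placebo still begins at their first dose of any study treatment.

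**Working it through.** The SAP gives no figure on this point, so there is none to reproduce. The check applies its formulas under an equal, constant true rate in every group.

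**Inputs**
- Time at risk T for a participant entering the extension at Week 48: 48 × 7 + 1 = 337 days (Section 10.1.3.2).
- T for a participant with last dose at Week 46 and full safety follow-up: 46 × 7 + 141 = 463 days (Sections 7 and 10.1.3.2).
- Antibody samples at Weeks 4, 8, 12, 16, 20, 24, 36 and 48 (Section 9.3.2). First positivity is placed at t = 7 × week. Its actual timing is not given, so a range is shown.

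**EAER, Categories 2 and 5.** Reported rate divided by true rate is t/T in the 'before' column and (T − t)/T in the 'on or after' column. For example, Week 16 with T = 337 gives (337 − 112)/337 = 225/337 = 0.67.

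| First positive | Before, T = 337 | On or after, T = 337 | Before, T = 463 | On or after, T = 463 |
|---|---|---|---|---|
| Week 4 | 0.08 | 0.92 | 0.06 | 0.94 |
| Week 12 | 0.25 | 0.75 | 0.18 | 0.82 |
| Week 16 | 0.33 | 0.67 | 0.24 | 0.76 |
| Week 24 | 0.50 | 0.50 | 0.36 | 0.64 |
| Week 36 | 0.75 | 0.25 | 0.54 | 0.46 |

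With conversion at Week 24, a true doubling afterwards would be reported as 2 × 0.50 = 1.0 times the reference rate when T = 337, and as 2 × 0.64 = 1.28 times when T = 463.

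**EAIR, Categories 2 and 5.** Let λ be the assumed true rate per year and s = t/365.25, with T also in years. Exposure runs from first dose to the first post-positivity event, or to T if there is none. With p = 1 − exp(−λ(T − s)), reported over true is p/(λs + p). For λ = 0.05, Week 16 and T = 337 days, s = 0.307 and p = 0.0303, so the ratio is 0.0303/(0.0153 + 0.0303) = 0.66. As λ goes from 0.05 to 2, the factor goes from 0.92 to 0.84 at Week 4, 0.66 to 0.54 at Week 16, and 0.25 to 0.21 at Week 36.

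**Dilution.** Categories 3, 4 and 6 are positive from Baseline, so outside the placebo-switch arm all their time belongs in the 'on or after' column. If they make up an assumed share q of it, the column's EAER factor is q + (1 − q)(T − t)/T. At Week 16 with T = 337, q = 0.25 gives 0.25 + 0.75 × 0.668 = 0.75, and q = 0.50 gives 0.83.

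**Placebo-switch arm (70 of 490 planned, Section 2.4).** Bimekizumab starts at Week 16, so countable events cover (337 − 112)/337 = 0.67 of the denominator, or 32/48 in weeks. That applies to always-negative switchers too. A switcher first positive at Week 24 has 'on or after' factor 169/337 = 0.50 and 'before' factor 56/337 = 0.17.

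**After the repair.** Dividing each column's events by the bimekizumab time in which they could occur returns the ratio to 1.00 for both EAER and EAIR.

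**The case against.** The SAP never states a denominator for this table by name. The unsplit reading comes from the general rule in Section 10.2.1 together with the absence of an exception. That section also describes time at risk as time during which an event could occur for the participant, so a programmer might split it unprompted. That is possible, but the rule as written points to Section 10.1, and Section 10.1 has no split. On placebo time, Section 3.3 bases first dose on the first injection whether active or not, and Section 3.2.1 names the first bimekizumab dose separately where it is meant.

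The table is descriptive, with no test or decision rule attached, and participant counts, percentages and event counts are not distorted. Both points stand and limit the consequence to the rates.

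A reader might infer more than the documents support:

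- *That the always-negative column is a sound reference.* It is not in the placebo-switch arm, where it is also deflated.
- *That a fourfold increase would vanish.* That needs conversion at Week 36, 337 days at risk and no Baseline-positive participants in the column. At 463 days the factor is 0.46, and conversion at Week 4 costs only 6% to 8%.
- *That every rate is divided by whole time at risk.* This is exact for the EAER. For the EAIR, participants with the event are cut at first occurrence but still counted from first dose, so the direction is the same.

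**Conclusion.** The point holds. Followed as written, the SAP understates the 'before' and 'on or after' EAER, and in the same direction the EAIR, for Categories 2 and 5. The 'on or after' EAER factor for these participants runs from 0.92 to 0.25 with 337 days at risk, and from 0.94 to 0.46 with 463 days, for first positivity between Weeks 4 and 36. These figures assume a constant, equal true rate. For the column as a whole the bias is smaller, to an extent that depends on how many participants are positive from Baseline.

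In the placebo-switch arm all three columns are understated, the always-negative one to about 0.67 at 48 weeks. The three columns are therefore not comparable as specified. The size in the actual data cannot be known from the SAP, because it gives neither the timing nor the frequency of conversion. Efficacy analyses and the other exposure-adjusted tables are not touched by the antibody split.

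**What to change.** Add a paragraph to Section 10.2.2, for this table only:

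- Start time at risk at the first bimekizumab dose in every column, including Category 1.
- For Categories 2 and 5, split it at the date of the first positive (Category 2) or first boosted (Category 5) result. Time before that date goes to the 'before' column, and time from that date to the 'on or after' column.
- For the EAIR, start the clock at the beginning of each column's interval and stop it at the first event within that column.
- Leave Section 10.1 unchanged for all other tables.

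Category 1 must be included. If it kept the Section 10.1 start, always-negative switchers would stay at 0.67 of the true rate while the repaired columns read the true rate, a spurious excess of 1/0.67 = 1.5-fold in that arm.

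The cost is one paragraph of SAP text and a few derived dates in the exposure dataset, with no new data collection.

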$$CI_{RD} = RD \pm Z_{1-\alpha/2} \times (SE_{RD})$$

where $Z_{1-\alpha/2}$ is the Z statistic for the corresponding level of alpha. For the risk difference confidence intervals calculated in this SAP, 1.96 will be used (corresponding to a two-sided alpha of 0.05 and 95% confidence interval). The risk difference and corresponding CI will be displayed as percentage.

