10.2.3 Other Safety topics of interest

The following are AEs considered to be other safety topics of interest that require special statistical analyses. Along with the tables described, there will be a table which displays the risk difference and 95% confidence intervals for each of the topics of interest in the Initial Treatment Period. A corresponding figure (with dot plots) will be prepared.

A by-participant listing of all AEs of safety topics of interest will be presented by type of safety topics of interest.

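### The EAIR confidence limits in SAP Section 10.2.1 are limits for a count, not for a rate per 100 subject-years; separately, the Wald risk-difference interval is correctly written but too narrow for sparse events

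*SAP*

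**What the plan says.** SAP Section 10.2.1 defines the EAIR as 100 x n / sum of T_Exp, that is, "adjusted for the exposure and will be scaled to 100 subject-years". It then states: "Exact Poisson 95% confidence intervals for incidence rates are calculated using the relationship between the Poisson and the Chi-square distribution". The limits are given as "LCL = \chi^2_{2n, \alpha/2} / 2" and "UCL = \chi^2_{2(n+1), 1-\alpha/2} / 2", "where n is the number of participants with a specific AE for the incidence rate of interest". The legend adds that n sets the "degrees of freedom for the chi-square quantile for the upper tail probability". Neither limit contains exposure or the factor 100, and nothing else in Section 10 rescales them. Section 10.2.2 puts the EAIR and its interval in every summary per 100 subject-years; the topic summaries in Section 10.2.3 are also per 100 subject-years.

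For risk differences, Section 10.2.1 gives the unpooled Wald standard error and states: "For the risk difference confidence intervals calculated in this SAP, 1.96 will be used". There is no rule for zero or very small counts. Section 10.2.2 applies the interval to TEAEs above 5% and to serious TEAEs by SOC and PT, with dot plots. Section 10.2.3 adds "a table which displays the risk difference and 95% confidence intervals for each of the topics of interest", again with a figure.

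**The concern.** An interval for a rate has to be on the scale of the rate. The printed limits are on the scale of the count, and the two scales agree only if total exposure is exactly 100 subject-years. Programmed as written, the limits fall too low when exposure is below 100 years and too high when it is above. Every EAIR table would be affected.

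The risk-difference question is different in kind. The formula is a recognised one. With no event on placebo, however, the placebo variance term is zero, so the interval treats the placebo risk as known. In tables of rare events against a placebo arm of 70, it may then exclude zero because of the method alone.

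**Working it through.** **Inputs.** Planned arms are 140, 140, 140 and 70 (Section 2.4). Two bimekizumab arms are pooled for the Initial Treatment Period (Section 3.6), giving comparisons of 280 v 70 and 140 v 70; 420 v 70 applies if all bimekizumab arms are combined. The Initial Treatment Period is 112 days (Section 10.1.1.2), and days are divided by 365.25 (Section 10.1). The SAP gives no safety event rates, so every event count and risk below is an assumption. Exposure is taken as complete.

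**The plan's own figure.** The two-sided 95% normal critical value is 1.95996, so 1.96 is right.

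**EAIR, one case in full.** Take n = 7 of 70 on placebo.
- Exposure: 70 x 112 / 365.25 = 21.5 subject-years.
- EAIR: 100 x 7 / 21.465 = 32.6.
- Printed limits: chi2(14, 0.025)/2 = 2.8 and chi2(16, 0.975)/2 = 14.4. The estimate lies outside.
- Multiplied by 100 / 21.465: 13.1 and 67.2.

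**EAIR, other cases.**

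| Assumed case | Subject-years | EAIR | Printed limits | Scaled limits |
|---|---|---|---|---|
| 5 of 70, 112 days | 21.5 | 23.3 | 1.6 to 11.7 | 7.6 to 54.4 |
| 10 of 140, 112 days | 42.9 | 23.3 | 4.8 to 18.4 | 11.2 to 42.8 |
| 20 of 280, 112 days | 85.9 | 23.3 | 12.2 to 30.9 | 14.2 to 36.0 |
| 30 of 420, 112 days | 128.8 | 23.3 | 20.2 to 42.8 | 15.7 to 33.3 |
| 30 of 490, 336 days | 450.8 | 6.7 | 20.2 to 42.8 | 4.5 to 9.5 |

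Three of these five printed intervals exclude their own estimate. At a true rate of 20 per 100 subject-years, exact coverage of the printed limits is 0.16 (140 participants), 0.002 (70) and 0.77 (420). The scaled limits cover 0.96 to 0.98.

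**Tail wording.** The printed subscripts are correct for lower-tail quantiles. Taken literally as upper-tail probabilities, they reverse the limits: for n = 7, LCL 13.1 and UCL 3.5 on the count scale. For n = 0 the lower limit would need a chi-square quantile on 0 degrees of freedom and should simply be 0.

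**Risk difference, one case in full.** Take 6/280 v 0/70.
- RD = 6/280 = 2.14%.
- SE = sqrt(0.02143 x 0.97857 / 280 + 0) = 0.865%.
- Wald: 2.14% ± 1.96 x 0.865% = 0.45% to 3.84%, which excludes zero.
- Newcombe: -3.19% to 4.60%. Fisher p = 0.60.

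With no placebo event, x events among n on bimekizumab exclude zero when x > 3.84 x (1 - x/n). At these arm sizes, 4 events are enough and 3 are not. For 4/420 v 0/70, Wald gives 0.02% to 1.88%, Newcombe -4.3% to 2.4%, and Fisher p = 1.0. For 0/420 v 0/70, Wald gives 0 to 0 and Newcombe -5.2% to 0.9%.

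**Exact Wald coverage at assumed equal risks.**

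| Risk | 140 v 70 | 280 v 70 | 420 v 70 | Chance of no placebo event |
|---|---|---|---|---|
| 1% | 97% | 85% | 70% | 49% |
| 2% | 92% | 80% | 76% | 24% |
| 3% | 91% | 87% | 87% | 12% |
| 5% | 93% | 92% | 91% | 3% |
| 10% | 94% | 94% | 93% | 0.1% |

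Newcombe coverage is 95% to 99% throughout.

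**The case against.** **On the EAIR.** The governing sentence speaks of incidence rates, names a standard method and follows directly on a rate scaled to 100 subject-years. An experienced programmer would probably add the missing step, and limits of 2.8 to 14.4 around 32.6 would be noticed in checking. No hypothesis test depends on these intervals. All of that is fair, and it makes this an omission in the write-up rather than a flaw of design. But the SAP gives explicit formulas and is the specification. The error is also not always conspicuous: for 280 or 420 participants over 16 weeks, exposure is 85.9 or 128.8 years, and the wrong limits look plausible. The full-exposure assumption does not matter to the conclusion. If the 7 events fall at mid-period, exposure is about 20.4 years, the EAIR 34.3, and the scaled limits 13.8 to 70.7. The tail wording is editorial, since reversed limits would hardly survive programming.

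**On the risk difference.** A reader might infer that this formula is wrong too, or that the interval collapses whenever placebo has no event. The SAP supports neither. The Wald interval is correctly stated, and choosing another is a choice of method. With no placebo event it becomes too narrow, but it has zero width only when neither arm has an event. The weakness is not uniform either: for 280 v 70, coverage is 96.2% at a 0.5% risk. One of the two AE risk-difference tables is limited to TEAEs above 5%, where Wald is close to nominal. The tables are descriptive, and counts are shown. What stands is the shortfall at risks of roughly 1% to 3% in the serious-TEAE and topics-of-interest displays.

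**Conclusion.** The EAIR limits are wrong as written and should be corrected. Followed literally, they give an interval on the wrong scale, off by the factor 100 / sum of T_Exp. In the assumed cases that factor runs from about 4.7 (70 participants, 16 weeks: 100 / 21.5) down to about 0.22 (490 participants, 48 weeks: 100 / 450.8). This conclusion does not depend on the assumed counts; only the sizes of the examples do.

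The risk-difference interval is a secondary matter and a recommendation. Its size rests on assumed event risks and on the planned arm sizes, and the worst figures (70% and 76%) apply only if all bimekizumab arms are combined against placebo.

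**What to change.** In SAP Section 10.2.1, write the EAIR limits as LCL = 100 x chi2(2n, 0.025) / (2 x sum of T_Exp) and UCL = 100 x chi2(2(n+1), 0.975) / (2 x sum of T_Exp), using the same T_Exp as the estimate. Describe the quantiles as lower-tail (cumulative), and state LCL = 0 when n = 0. This changes SAP text only and has no statistical cost.

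As a further improvement, specify a Newcombe or Miettinen-Nurminen interval for the risk differences of serious TEAEs (Section 10.2.2) and safety topics of interest (Section 10.2.3), including their dot plots. Both are standard software options. The downside is wider intervals for rare events.
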